There will be rare situations when a participant is enrolled and randomized in the study, but is unable to begin or complete the 8-week intervention due to unforeseen changes in their life such as the death of a family member or the sudden need for medical treatments. In such situations, participants will be given the option to: (a) delay their participation in the 8-week intervention portion of the study, (b) withdraw from the 8-week intervention, but undergo one or more of the post-intervention data collection meetings, or (c) withdraw from all aspects of the study. Trained study staff will identify and track such situations in REDCap.

If participants choose option (a), they will **not** be re-randomized. Rather, researchers will invite them to an 8-week intervention course/ condition to which they were originally randomized, but that is scheduled to occur in a later time-frame.

Research staff will repeat screening to determine continued eligibility.

- If participants remain eligible, research staff will repeat baseline assessments within 8 weeks of the participant's delayed start of the 8-week intervention.
- If participants become ineligible---, reason(s) for ineligibility will be documented.

The analyst will compare and report the results of repeated baseline measures for subjects who choose option (a) and remain eligible for the study. If the differences between the repeated baseline measures are not significant, the first set of values will be used in inferential analyses. If the differences between the repeated baseline measures are significant, the second set of values (those most proximal to the intervention delivery) will be used in inferential analysis. A description of this will be included in all reports.

Research Outcome Data Collection. Trained research assistants will collect all data. They will be trained to accurately collect and manage data and to interview older adults in ways that are non-threatening, friendly, and respectful. Data will be derived from in-person interviews, observations, monthly fall calendars, and objectively measured PA parameters from accelerometers within participant's commercially available PA-monitors.

In-person interviews include scripted, structured interviews asking questions from these validated tools (all widely used) at the following time points:

- Baseline only: Demographic*
 - Biological
- Baseline; immediately post-intervention; 6 months' post-intervention; and 12 months post-intervention:

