9.2 EXCLUSION CRITERIA

Exclusion criteria for participation in this study include:

- Lower extremity surgery within the past 6 weeks
- Inability to walk
- Formal diagnosis of neurocognitive impairment or Callahan Dementia Screener score of < 5.

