We will offer to coordinate and subsidize transportation to data collection and intervention meetings, upon request from participants in need.

Participants will receive \$50.00 after each of the four PA data collection periods (approximately 7 days each) and \$20.00 after each of the 4 data collection meetings (interviews).

The 8-week intervention meetings will be free of charge and participants will be encouraged to keep and use workbooks, ankle weights, and PA-monitors they receive as part of this intervention.

Forty participants will also be invited to participate in a semi-structured interview within 6 months of completing the study and will receive an additional \$20.00 after that interview.

Therefore, the total possible compensation for participating in the study ranges from \$280.00 to \$300.00.

Compensation will go directly to the participant and Research Experience Points will not be awarded.

Compensation schedule. Participants will be reimbursed immediately after each data collection period as scheduled bellowed:

- Structured Interview 1 (Baseline): \$20.00
- Structured Interview 2 (Immediately post-intervention): \$20.00
- Structured Interview 3 (6 months post-intervention): \$20.00
- Structured Interview 4 (12 months post-intervention): \$20.00
- PA data collection period 1: (Baseline): \$50.00
- PA data collection period 2: (Immediately post-intervention): \$50.00
- PA data collection period 3: (6 months post-intervention): \$50.00
- PA data collection period 4: (12 months post-intervention): \$50.00
- PROCESS Evaluation: Post-study completion: \$20.00
 - 25 to 30 participants (from each condition) will be selected, at random, to participate in a 30-45-minute interview addresses barriers and facilitators of intervention implementation and effect.

CHAPTER 13 – WITHDRAWAL OF PARTICIPANTS

13.1: WITHDRAWAL CIRCUMSTANCES

We anticipate all withdrawals from our study will be voluntary, based on our two pilot studies during which there were no involuntary withdrawals (out of 130 participants).

13.2: WITHDRAWAL PROCEDURES

When participants withdraw from the intervention, but continue to participate in data collection, we will:

- Document their withdrawal from the intervention and reason(s) for withdrawal (e.g., change in schedule, illness, family responsibilities)
 - We will use intention to treat, such that data from these participants will be included in the analysis.

13.3: TERMINATION PROCEDURES

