<https://sites.google.com/a/umn.edu/redcap-help/>). Both Fitabase and REDCap meet privacy and security required when conducting research responsibly. Were someone to gain access to the physical activity data, they would not be able to identify the participants because these files use unique Fitbit identification numbers only, not study identification numbers or personally identifying information. If this unlikely event happens, we will report it using procedures outlined above. Steps would then be taken to identify how the breach occurred and what needs to be done to correct it.

An example of a serious adverse event includes the possibility of physical or psychological distress during the administration of the Short Physical Performance Battery (SPPB), an observational measure of functional strength and balance. To minimize this risk, research staff are trained and their continued competence to perform the SPPB, according to a standard protocol, is monitored monthly. The standardized protocol includes instructions to elicit participant's comfort and willingness to proceed with each movement. If the participant or the research assistant are not comfortable proceeding, the movement is not pursued. Participants are offered a verbal and written copy of their SPPB scores. The SPPB is established as a safe test to use across older populations. Participants in our studies have not had serious adverse events, expected adverse events or unexpected adverse events during the SPPB. If this unlikely event happens, we will report this using procedures outlined above. Steps would also be taken to identify how the event occurred and what needs to be done to correct it.

Another example of a serious adverse event would be the death of a participant from chronic heart failure. While viewed as unexpected and unrelated to the behavioral intervention, death

from heart failure would nonetheless be a reportable, serious event. No further steps would be taken except to review, grade and report the event using procedures outlined above.

An example of an unanticipated problem would be if a participant became immobile during their participation in the study. As immobility is an exclusion, we would withdraw the subject from the study. This event will be reviewed, graded, and reported using procedures outlined.

Assessment of External Factors

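### Section 18.2 would withdraw a participant who becomes immobile after randomization from the study; the plan should state that outcome follow-up continues

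*Combined protocol and SAP*

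**What the plan says.** Section 9.2 lists "Inability to walk" among the exclusion criteria. Section 18.2 returns to it in its examples of reportable events, where a participant becomes immobile during the study: "As immobility is an exclusion, we would withdraw the subject from the study". The event is then reviewed, graded and reported. Nothing is said about interviews, fall calendars or PA capture afterwards.

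Three other places bear on the point.

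- **Section 5.2** gives options to a randomized participant who cannot begin or complete the intervention. One is to "withdraw from the 8-week intervention, but undergo one or more of the post-intervention data collection meetings"; another is to "withdraw from all aspects of the study". A third is to delay, with rescreening. If a delayed starter is then found ineligible, the plan says only that the reason is recorded.
- **Chapter 13.** Section 13.1 states: "We anticipate all withdrawals from our study will be voluntary". Section 13.2 opens its procedure with "When participants withdraw from the intervention, but continue to participate in data collection, we will" and then says "We will use intention to treat, such that data from these participants will be included in the analysis".
- **Section 17.1** includes all cases whatever their attendance or attrition. It expects little missing data, at similar rates across conditions, but recognises that missingness may be linked to severe illness. For that reason it plans two sensitivity analyses: complete cases, and worst case carried forward.

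**The concern.** An entry criterion decides who is randomized. Used afterwards to end a participant's time in the study, it makes follow-up depend on what happened after randomization. Immobility is not a neutral event here. It bears directly on PA, the primary outcome, and it may follow a fall, a secondary outcome: Section 2.2 itself notes that serious fall injuries reduce mobility and QOL. If collection stops at that moment, the missing values are informative.

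The analysis plan cannot repair this later. Including all cases is a rule about analysis, and imputation substitutes an assumption for an observation. The decision has to be made at the data-collection stage.

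**Working it through.** The plan gives no figure for immobility or for staff-initiated withdrawal, so there is nothing of its own to reproduce. The check has three steps.

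**1. The routes out of the study, side by side**

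| Route | Who decides | Outcome collection afterwards | Reached by the intention-to-treat sentence in 13.2? |
|---|---|---|---|
| 5.2, option (b) | participant | at least partly continues | yes |
| 5.2, option (c) | participant | ends | no |
| 5.2, delayed starter ineligible on rescreening | staff | not stated; reason recorded | only if collection continues |
| 18.2, newly immobile | staff | not stated; plain reading is that it ends | not on the plain reading |

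The plain reading comes from the object of the verb. Section 5.2 distinguishes leaving the intervention from leaving everything, and Section 18.2 names the study, not the intervention. Section 13.1 foresees only voluntary exits, so Chapter 13 supplies no procedure for the last two rows.

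**2. How many people**

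Inputs: 0 involuntary withdrawals among 130 pilot participants (Section 13.1); 308 randomized, and 15% attrition at 12 months against 7% at 6 months in the preliminary studies (Section 17.2).

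- One-sided 95% upper limit for 0 of 130: 1 − 0.05^(1/130) = 0.0228, or 2.3%.
- Applied to the trial: 0.0228 × 308 = 7.0 people.
- If pilot follow-up was only half as long (an assumption, suggested by the 6-month figure): 1 − (1 − 0.0228)² = 0.0450, and 0.0450 × 308 = 13.9 people.
- Expected attrition from all causes: 0.15 × 308 = 46.2. Seven people would be 7 / 46.2 = 15% of that.

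The range is therefore 0 to about 7, or about 14 under the longer-exposure assumption. The pilot count covers all involuntary withdrawals, not immobility alone, and the documents do not say whether the pilots applied this rule.

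**3. Effect on a factor contrast**

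Let p₁ and p₀ be the proportions withdrawn for immobility at the two levels of a factor, and let g be the amount by which their mean outcome lies below that of everyone else, taken as equal at both levels. With these people included, the mean at level k is m_k − p_k·g; without them it is m_k. Then:

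shift in the contrast from leaving them out = (m₁ − m₀) − [(m₁ − p₁g) − (m₀ − p₀g)] = (p₁ − p₀) × g

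The shift is zero when p₁ = p₀ and changes sign when the ordering of the rates reverses. The documents give none of p₁, p₀ or g, so no value can be computed without inventing inputs.

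**The case against.** The strongest reply is that the quoted sentence carries little weight. It is a conditional illustration in a list about event reporting, while withdrawal is governed by Chapter 13. The plan also foresees this kind of missingness: Section 17.1 names severe illness as a likely cause and attaches sensitivity analyses to it. All four conditions share the exercise protocol, the monitor and the same contact time (Table 3 in Section 4.1), so the documents give no reason to expect immobility rates to differ by factor. Monitor PA may also mean little for someone who cannot walk.

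Most of this stands, and it is why the point is small. It does not close the gap. Chapter 13 has no procedure for a staff-initiated exit, so the example is the only text that addresses the case. The sensitivity analyses work on whatever was collected.

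A reader might infer that Section 18.2 expressly orders data collection to stop. It does not say so in words. The options in Section 5.2 are participant choices for people who cannot begin or complete the intervention, and Section 18.2 does not use the wording of option (c). A participant who becomes immobile during the 8 weeks might even be handled under option (b).

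Two general matters are not counted here because they apply to every dropout: a visit-specific ANCOVA needs a value at that visit, and worst case carried forward is not defined.

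**Conclusion.** The point holds as a cheap improvement. As written, and on its plain reading, the example ends outcome collection for a randomized participant because of an event related to the outcomes, and no other section supplies a different rule. The same silence applies to a delayed starter found ineligible on rescreening.

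The likely number is small: 0 to about 7 of 308 if the pilot experience carries over, or about 14 if pilot follow-up was half as long. Under the simple model above, bias is zero at equal rates across factor levels; otherwise neither its size nor its direction can be estimated from the documents.

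A reader might go further and conclude that the plan breaks its intention-to-treat commitment, or that the PA result will be distorted by a stated amount. Neither follows. Section 13.2 limits its commitment to people who remain in data collection, and Section 17.1 keeps all cases in the analysis, so this is a gap between passages and not a direct contradiction. Any figure for PA bias would rest on assumed immobility rates and assumed PA levels.

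**What to change.** Reconcile the Section 18.2 example with Sections 5.2, 13.1, 13.2 and 17.1 by adding one data rule. A participant withdrawn by staff, or found ineligible after randomization:

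- remains in outcome follow-up (fall calendars, home or phone interviews, QOL, and PA where feasible) unless consent is withdrawn;
- is analysed in the condition to which they were randomized;
- is reported by condition, with the reason.

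Decisions about taking part in the exercises stay with the existing safety process; this rule concerns data only.

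The change is to protocol wording. Mailed fall calendars (Section 5.2), home data-collection meetings (Section 19.1) and outcome visits after leaving the intervention (Section 5.2, option b) already exist. Phone interviews were introduced only for the Coronavirus period (Section 5.2), so the new text should permit them here. The downside is a few extra follow-up contacts with participants who are harder to assess, and monitor PA that may have limited meaning for them.

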20.2 COMPENSATION OF RESEARCH RELATED INJURY

Not Applicable

20.3 CONTRACT LANGUAGE

Provide a copy of the contract language, if any, relevant to compensation for research-related injury.

20.4: WAIVER OR ALTERATION OF CONSENT PROCESS

Not Applicable

20.5: NON-ENGLISH SPEAKING PARTICIPANTS

Not Applicable

20.6: PARTICIPANTS WHO ARE NOT YET ADULTS

Not Applicable

20.7: COGNITIVELY IMPAIRED ADULTS, OR ADULTS WITH FLUCTUATING OR DIMINISHED CAPACITY TO CONSENT

Not Applicable

20.8: ADULTS UNABLE TO CONSENT

Not Applicable

CHAPTER 21 – SETTING

21.1: INTERNATIONAL RESEARCH

Not Applicable

21.2: COMMUNITY-BASED PARTICIPATORY RESEARCH

We will conduct the proposed study in community centers located in the four quadrants of Minneapolis (see letters of support from [name], [name], and [name] within the supporting documents in ETHOS).

All research will be performed by UMN key personnel and staff, under the auspices of the UMN IRB. Community centers will host meetings during which UMN research staff will collect data and conduct intervention meetings. We chose these 4-community center locations for 4 primary reasons. First, we have longstanding partnerships (3+ years) with each center that include the conduct of our preliminary studies. Second, each community center has goals that are congruent with this proposal's objective. Third, each center serves ethnically and socioeconomically diverse populations. Fourth, each center has environments conducive to small group discussions and practicing fall-reducing PA, is accessible via public transportation, and has free parking.

Each center will host the small-group intervention meetings during 2 to 4 of the 13 study waves. Community-research teams will establish times and days for intervention meetings one month prior to the first intervention meeting. Although meetings will be hosted within the community centers, staff there will not coordinate participant attendance, collect data, lead, or participate in the small group meetings. The centers are listed below:

- Sabathani Community Center, Minneapolis, Minnesota
- Volunteers of America, Minneapolis, Minnesota
- Southwest Community Center, Minneapolis, Minnesota
- Park Elder Center, Minneapolis, Minnesota
- East Side Neighborhood Services, Minneapolis, Minnesota
- St. Paul Parks and Recreation locations including Highland Park Community Center; Linwood Community Recreation Center, Palace Community Center
- Minneapolis Public Libraries including Hosmer and Pierre Bottineau
- Lutheran Redeemer Church, Saint Paul, Minnesota
- West 7th Community Center, Saint Paul, Minnesota
- University of Minnesota Urban Research and Outreach-Engagement Center, Minneapolis, Minnesota

We chose these community center locations for 4 primary reasons. First, we have longstanding partnerships (3+ years) with each center that include the conduct of our preliminary studies. Second, each community center has goals that are congruent with

this proposal's objective. Third, each center serves ethnically and socioeconomically diverse populations. Fourth, each center has environments conducive to small group discussions and practicing fall-reducing PA; is accessible via public transportation; and has free parking.

The PI and community center leaders will meet prior to the beginning of the study and then quarterly and as-needed meetings throughout all phases of this project. Similar to our preliminary studies, the research – community teams will review recruitment and retention plans; establish communication procedures for the reservation of private rooms for data-collection and intervention meetings; and local dissemination based on each center's preferences. Each year, one of the quarterly meetings will include a project progress report.

Additionally, the research team will interview a representative from each community center about facilitators and barriers to providing this program in the future. Interview topics will be framed using the *reach- effectiveness –adoption- implementation- maintenance* framework (RE-AIM), a system for evaluating this intervention's potential for translation.

Finally, we will seek advice about our community engagement at least every six months throughout the study from [name] and experts in the UMN, CTSI's *Community Engagement to Advance Research and Community Health* (see letter of support).

21.3: RESEARCH SITES

The research will be conducted and administered through the University of Minnesota, School of Nursing. Potential research participants will be identified and recruited from the communities within Minneapolis, primarily through newspaper advertisements.

Research procedures will be performed primarily in the University of Minnesota, Nursing Research Space.

- The School of Nursing is housed in Weaver-Densford Hall, which includes approximately 35,000 square feet of teaching, research, and office facilities. Space for [name] and her research team is also available at the [name] located approximately four city blocks from faculty and administrative offices. Available resources within the School of Nursing include offices, conference rooms, telephone, WebEx, fax, and secure confidential data storage areas.
 - [name] office in the School of Nursing is approximately 125 square feet and is equipped with a personal computer (including the necessary statistical software), laser printer, Web camera, telephone access, and ample locked file space to conduct the proposed evaluation. The computer has LAN access
 - [name] and trained study staff for this project also have 4 research offices at the [name] on campus, with work space, computers, telephone access, and secure file cabinets for

Additionally, private rooms will be used by trained research staff to conduct data collection interviews and deliver the small group intervention. Private rooms will be reserved for these meetings within the following community centers, per participant availability and intervention schedules. These community centers do not have site-specific regulations or customs affecting the research. Because each community center is not conducting the research, they do not require local scientific or ethical review:

CHAPTER 22 – MULTI-SITE RESEARCH

N/A

CHAPTER 23 – REFERENCES

1. Centers for Disease Control and Prevention. Reporting system (WISQARS). *National Center for Injury Prevention and Control, Centers for Disease Control and Prevention* (producer). Available from: URL: www.cdc.gov/ncipc/wisqars.
